LPO	Last Patient Out
MACE	Major Adverse Cardiac Events
MBO	(Model) Professional Code for Physicians in Germany
MCP-1	Monocyte chemoattractant protein-1 (= CCL2)
MedDRA	Medical Dictionary for Regulatory Activities
mRNA	Messenger Ribonucleic Acid
n, N	Number
PASI	Psoriasis Area and Severity Index
PDE / PDE4	Phosphodiesterase / Phosphodiesterase 4
PGA	Physician Global Assessment
PP	Per Protocol (set)
PPP	Palmoplantar pustulosis
PPPASI	Palmoplantar Pustulosis Psoriasis Area and Severity Index
PPPASI 50 / 75	50% / 75% decrease in PPPASI
PsA	Psoriasis Arthritis
PT	Preferred Term
PUVA	Psoralen plus ultraviolet A radiation
qPCR	Real-time Polymerase Chain Reaction on reverse transcribed mRNA
RMP	Risk Management plan
SAE	Serious Adverse Event
SAP	Statistical Analysis Plan
SOC	System Organ Class
SOP	Standard Operating Procedure
sP-selectin	Soluble P-selectin
ThX	T Helper Cell X

TNF	Tumor Necrosis Factor
TEAE	Treatment emergent AE
ULN	Upper limit of normal
UVB	Ultraviolet B
V	Visit
VAS	Visual Analogue Scale
WHO	World Health Organization

Definitions

Baseline	Data collected for all patients at the beginning of a clinical study before any study treatment. These data include demographics, such as age and gender, and study-specific measures.
Eligible Patient	Any potential participant who upon entrance into the treatment phases of the study meets all of the inclusion criteria and none of the exclusion criteria set forth in the protocol and had signed a valid Ethics Committee (EC) approved informed consent form.
End of Study / Study Completion Date	Final date on which data is collected (i.e. date of the last visit of the last patient).
Screening	Evaluation of patients for participation in a clinical study according to inclusion and exclusion criteria.

6 Introduction

Psoriasis in difficult to treat locations includes visible and therefore stigmatizing body regions such as the hands, the face and the scalp. Other difficult to treat areas may impact the daily life aspects and function such as palms and soles and / or nails. Under normal conditions, these locations require particular management and have a significant impact on the health-related quality of life (physical, functional, emotional impact) (4-6). As this is such an important factor for the patients it is often higher ranking than corresponding disease indexes.

6.1 Background and Rationale

Palmoplantar pustulosis (PPP) is a rare condition in which erythematous and scaly plaques studded with sterile pustules persist on the palms or soles. The disease is chronic and very resistant to treatment. It is much more common in those who smoke (or have smoked in the past). PPP is a disease of adults and is rare in children. It usually starts in the fifth or sixth decade of life, although age of onset can also be earlier.

In most series, there has been a predominance of women. The disease presents itself with one or more well-delineated scaly erythematous plaques. Within this plaque, pustules are present, usually 2-5mm in diameter. Fresh pustules are yellow; older ones are yellow-brown or dark brown as the pustule dries up. Eventually, the desiccated pustule is exfoliated. Usually, pustules in all stages of evolution are seen. Itching is variable, but often serious; often, the patients report a 'burning' discomfort in the lesions. On the hands, the thenar eminence is the predilection site. On the feet, the instep, the medial or lateral border of the foot at the level of the instep, or the sides or back of the heel are frequently involved. A striking symmetry of the lesions on the hands or feet is common, but sometimes a solitary lesion may persist for weeks or months before other lesions appear. Additionally, patients are often unable to walk or to work due to the pain and thus are severely affected in activities of daily life (7).

Palmoplantar pustulosis is a therapeutically challenging condition that can significantly impact patient quality of life (8). It often affects smokers, but quitting smoking does not always help clear the disease. Apart from intense topical therapy (with or without occlusion), phototherapy, and psoralen plus ultraviolet A (PUVA), oral retinoids (acitretin) have traditionally been the first drug of choice. Phototherapy including PUVA therapy has the disadvantage, apart from cancerogenicity, that it has to be performed several times per week at an outpatient clinic or a private practice of a dermatologist. Acitretin is usually not given to girls and women of childbearing potential due to its teratogenic potential that persists for up to three years after discontinuation of the drug. Methotrexate or cyclosporine have been described to be effective in PPP in some patients as well (9-12). Alternative treatment options for patients with PPP who do not respond to conventional antipsoriatic therapies include the use of antimycotics (13) or antibiotics (14), which have been described in single case reports and studies. However, oral alitretinoin treatment has recently been proven not to be effective (15).

Several biologics that have been approved for plaque-type psoriasis have been tried in small case series or small studies in the treatment of PPP.

Ustekinumab, a monoclonal antibody targeting Interleukin (IL)-12/23 has been tried in the treatment of PPP, but results have been ambiguous. In a case series of four patients, two failed to improve (16). Bissonnette et al. (17) were not able to show clinical benefit with licensed doses of ustekinumab, while others recently presented a series of five, respectively nine, case reports successfully treated with ustekinumab (18;19).

A small placebo-controlled pilot study (n=15) with etanercept, a fusion protein targeting Tumor Necrosis Factor (TNF)- α , at a dose of 50 mg twice weekly, showed a statistically significant difference in Palmoplantar Pustulosis Psoriasis Area and Severity Index (PPPASI) response

at 24 weeks. At 12 weeks etanercept was numerically, but not statistically significantly better than placebo (20).

Alefacept is approved for plaque-type psoriasis in the United States but not in Europe and has been reported to be moderately effective in PPP with reductions in PPPASI of 49,6% after 16 weeks of treatment (21).

Despite the impact of PPP on daily activities including the ability to work, few clinical studies address treatment, and there is a lack of data and quality-of-life assessment during therapy beyond anecdotal case reports and small studies as described above (9;10;13;14;16-18;20;21).

Only Acitretin, Dapsone and glucocorticosteroids have the approval for the treatment of pustular skin diseases, and no other systemic antipsoriatic treatment has been approved for PPP.

Biologics are approved for plaque-type psoriasis and/or psoriasis arthritis, and they have also been described in some investigations to be successful in patients with PPP (17;18;20;21). However, there are no published phase III trials of biologics in the indication PPP, and treatment of PPP with biologics or traditional antipsoriatic drugs, with the exception of acitretin, can only be performed in an off-label setting.

Moreover, treatment of PPP often does not achieve a lasting good clinical response or may have to be discontinued due to side effects.

Apremilast (Otezla®, marketing authorization holder Celgene Europe Ltd., approved for treatment of Psoriasis and Psoriasis Arthritis in Europe), an oral small-molecule inhibitor of phosphodiesterase 4 (PDE4), works intracellularly to modulate a network of pro- and anti-inflammatory mediators. PDE 4 is a cyclic adenosine monophosphate (cAMP)-specific phosphodiesterase (PDE) and the dominant PDE in inflammatory cells. Inhibition of PDE4 elevates intracellular cAMP levels, which in turn downregulates the inflammatory response by modulating the expression of TNF- α , IL-23, and other inflammatory cytokines. Elevation of cAMP also increases anti-inflammatory cytokines such as IL-10. These pro- and anti-inflammatory mediators have been implicated in psoriasis and psoriatic arthritis. Interestingly, apremilast has anti-inflammatory effects on a wide variety of cell types. Not only does it exert anti-inflammatory effects on T-cells, but also on immune cells of the innate immune system including neutrophils and on cells mediating the connection of innate and adaptive immune system such as plasmacytoid dendritic cells (22). In line with the importance of PDE4 on the regulation of a wide variety of cell types and cytokines, apremilast affects a number of cytokines. It can reduce production of both Th1 and Th17 cytokines (23). In addition, it influences the cytokines that are considered to be important mediators of the crosstalk between innate and adaptive immune functions: TNF α , IL-1 and interferons (22-24). For example, apremilast has been shown to increase levels of the anti-inflammatory IL1 receptor antagonist alpha in patients with psoriatic arthritis treated with apremilast, while it reduced concentration of monocyte chemoattractant protein-1 (MCP-1) (also called chemokine (C-C motif) ligand 2 (CCL2)) (23). Interestingly, C-C chemokine receptor type 2 (CCR2), a receptor of CCL2 on neutrophils, has recently been shown to be crucial in the recruitment of neutrophils into joints in rheumatoid arthritis (25).

This wide spectrum of antiinflammatory actions of apremilast might be important in the therapy of PPP. PPP is characterized by a strong inflammation in lesional skin, in which both the innate and adaptive immune systems are represented (26). While PPP has great similarities in the cytokine profiles compared to plaque-type psoriasis, including overexpression of IL17 and TNF α (26;27), neutrophils are more prominent both clinically (pustules) and in histopathology in PPP compared to plaque-type psoriasis.

Apremilast has already proven to be effective in the treatment of plaque-type psoriasis and psoriatic arthritis, and in a sub-analysis also in palmoplantar involvement of plaque-psoriasis

(28). Given the wide overlap of clinical, immunological and histological features of PPP and plaque-type psoriasis in conjunction with the observation that apremilast also effectively targets the innate immune system (e.g. neutrophils) it may be speculated that apremilast can successfully be used in the treatment of PPP.

The planned study is a multicenter, open label, single-arm pilot study intended to gain information on safety, clinical efficacy and the mechanistical effects of apremilast on PPP.

6.2 Potential Risks and Benefits

According to the 'summary of the risk management plan (RMP) for Otezla® (apremilast)' (29), by blocking the action of PDE4, apremilast reduces the symptoms of psoriasis and psoriasis arthritis. Because of exclusion of patients with moderate / severe kidney disorders, liver disorders, children and pregnant or breastfeeding patients from clinical trials, there is no information on safety or effectiveness of Otezla® for these patients. However, these patient groups will also be excluded for the clinical study presented here.

Important identified risks include:

- weight decrease in patients with Body Mass Index (BMI) <20 kg/m²
- depression

Important potential risks include:

- inflammation of blood vessels (vasculitis)
- risk of triggering suicide (suicidal thoughts)
- tumors (malignancies)
- nervousness and anxiety
- serious infections
- major heart problems (major adverse cardiac events [MACE] and tachyarrhythmia)
- effects on the developing child if used during pregnancy

For more detailed information on these identified and potential risks please refer to the 'summary of the risk management plan (RMP) for Otezla® (apremilast)' (29) and the 'Rote Hand Brief' (30).

Otezla® has been approved for the treatment of patients with moderate to severe plaque psoriasis and for the treatment of patients with active psoriatic arthritis. Overall, no serious safety issues are associated with Otezla® and the benefit-risk profile for Otezla® is acceptable and the risks can be mitigated through professional labeling.

7 Study Objectives and Purpose

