Criteria for Exclusion	
General
 
 • Pregnant or breast-feeding women • Current or history of psychiatric disease that would interfere with the ability to comply with the study protocol or give informed consent • Patients known to have had a substance abuse (drug or alcohol) problem within the previous 12 months • Individuals who are involved in the organization of the study • Patients who are in any way dependent on the investigator • Patients who are participating in a clinical study • Relatives, partner or staff of any clinical site personnel 
Disease-related
 
 • Evidence of skin conditions (e.g. eczema) other than PPP / psoriasis that would interfere with evaluations of the effect of study medication on PPP or psoriasis. • Laboratory values available from routine blood test taken within 8 weeks prior to screening with any of the following: 
 ○ Serum creatinine $>1.4 \times$ upper limit of normal (ULN) for age and gender ○ Estimated Glomerular Filtration Rate (eGFR) $< 30 \text{ mL/min}/1.73 \text{ m}^2$ according to the CKD-EPI equation • Pustular psoriasis lesions on the part of body other than hands or feet • Significant concurrent medical conditions at the time of screening, including: 
 ○ Risk factors for renal toxicity (renal inflammation) ○ Severe hepatic dysfunction ○ Unstable angina pectoris ○ Uncompensated congestive heart failure ○ Severe pulmonary disease requiring hospitalization or supplemental oxygen therapy ○ Immunodeficiency disorders: primary or secondary ○ Known positive HIV test result, hepatitis B surface (HBS) antigen or hepatitis C (HCV) test result ○ Uncontrolled Insulin-dependent diabetes mellitus ○ Cancer or history of cancer (except for resected cutaneous basal cell or squamous cell carcinoma) in the last 5 years ○ Open cutaneous ulcers • Any condition that, in the judgment of the investigator, might cause this study to be detrimental to the patient. 
Medication-related
 
 • Ultraviolet B (UVB) therapy, topical steroids, topical calcineurin inhibitors, topical Vitamin A or D analog preparations, or anthralin within 14 days of baseline • Exceptions: low potency topical corticosteroids (class I and II, according to European classification for potency of topical corticosteroids) will be allowed as therapy for the face, groin, axillae in accordance with the manufacturer's suggested usage dose

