Ethical Considerations	
This study will be conducted in accordance with applicable laws and regulations including, but not limited to, the ICH E6 guideline and the ethics principles that have their origins in the Declaration of Helsinki. The independent ethics committee and the competent authority must review and approve the study before any patients are enrolled. Consent must be obtained from the patient using the approved informed consent form (ICF) before any procedures specified in the protocol are performed.
 
The data acquisition meets all requirements of data protection for each individual patient, since all patient-related documentation can only be identified by a patient identification number. All personal information of the patient is accessible only to the treating physician.

Study Flow Chart

Phase	Screening	Treatment Phase					Early Termination
		V2 Baseline	V3	V4	V5 End of Study		
Visits	V1						
Week	-4 -- 1	0	4	12	20		
Day	-28 -- 1	0	28 ± 4	84 ± 4	140 ± 7		
In- / exclusion criteria	x	x	-	-	-	-	-
Pregnancy test ¹	x	x	x	x	x	x	
Informed consent	x	-	-	-	-	-	
Demography, educational status	x	-	-	-	-	-	
Medical and psoriasis history, prior medication	x	-	-	-	-	-	
PsA, comorbidity	x	x	-	x	x	x	
Concomitant medications	x	x	x	x	x	x	
Nicotine anamnesis	x	-	-	-	x	-	
Physical examination incl. weight and height ² (BMI)	x	x	-	-	x	x	
Vital signs ³	x	x	x	x	x	x	
Results of routine blood test / urinalysis available ⁴	x	-	-	-	-	-	
Investigator assessments							
PASI	-	x	x	x	x	x	
PPPASI	x ⁵	x	x	x	x	x	
PGA	-	x	x	x	x	x	
H&F PGA	-	x	x	x	x	x	
Dynamic H&F PGA	-		x	x	x	x	
Pustules count	-	x	x	x	x	x	
Patient reported outcomes							
VAS (pruritus / itch and discomfort / pain) on hands and feet	-	x	x	x	x	x	
DLQI	-	x	-	x	x	-	
Photographs ⁶ (optional)	-	x	-	-	x	-	
Serum and plasma	-	x	x	x	x	x	
Biopsies ⁷ (optional sub-study)	-	x	-	-	x	x	
Documentation for drug accountability and treatment compliance	-	x	x	x	x	x	
Medication dispensing ⁸	-	x	x	x	-	-	
Return of study medication	-	-	x	x	x	x	
AEs / SAEs	x	x	x	x	x	x	
Reason for discontinuation						x	

1. Urine pregnancy test for female patients of childbearing potential
2. Only at V1: height
3. Sitting blood pressure and pulse rate
4. Within the ranges given in the exclusion criteria **not older than 8 weeks** prior to screening
5. For inclusion PPPASI must be ≥ 12
6. From both hands and feet (optional)
7. Two lesional biopsies from feet or hands (optional)
8. Including instructions for medication intake

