9.1 Inclusion / Exclusion Criteria

The investigator must ensure that all patients who meet the following inclusion and exclusion criteria are offered enrolment in the study. Patients will be enrolled if all inclusion and none of the exclusion criteria are met. All patients screened to participate in the study will be documented and the reason for study exclusion will be documented to avoid enrolment bias.

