9.1.1 Inclusion Criteria

- Male and female patients aged 18 years or more at screening visit.
- Patients with chronic PPP (disease history of at least 6 months of diagnosis), who are eligible for treatment with systemic therapy defined as having PPP inadequately controlled by topical treatment and / or phototherapy and / or previous systemic therapy
- Patients with chronic moderate to severe PPP defined as patients with a PPPASI ≥ 12 with or without concomitant plaque-type psoriasis
- Negative result of a urine pregnancy test taken at screening and at baseline for all women, except those who are surgically sterile or at least 1 year postmenopausal (i.e. at least 12 consecutive months with amenorrhea without other known or suspected medical cause)
- Willingness and capability of using a highly effective contraceptive measures from Screening visit until the end of at least one menstrual cycle (but not less than 28 days) following discontinuation of apremilast as defined below:
 - Female patient of childbearing potential (fertile, following menarche and until becoming post-menopausal unless permanently sterile) using a highly effective method of contraception OR female patients of non-childbearing potential (surgically sterilized [e.g. hysterectomy, bilateral salpingectomy and bilateral oophorectomy] or post-menopausal)
 - Male patient, and their female partner of childbearing potential, using a highly effective method of contraception
 - Adequate contraceptive method defined as:
 - A method with less than 1% failure rate (e.g. permanent sterilization, hormone implants, hormone injections, some intrauterine devices, or vasectomized partner)
- OR
 - The use of two methods of contraception (e.g. one barrier method [condom, diaphragm or cervical/vault caps] with spermicide and one hormonal contraceptive [e.g. combined oral contraceptives, patch, vaginal ring, injectables and implants])
- Patient is capable of understanding and giving written, voluntary informed consent before study screening.
- Willingness and capability of complying with all study procedure requirements, as per the Investigator's judgment (e.g. patient able to swallow the apremilast tablets, blood sampling).

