9.1.2 Exclusion Criteria

General

- Pregnant or breast-feeding women.
- Current or history of psychiatric disease that would interfere with the ability to comply with the study protocol or give informed consent.
- Patients known to have had a substance abuse (drug or alcohol) problem within the previous 12 month
- Individuals who are involved in the organization of the study
- Patients who are in any way dependent on the investigator
- Patients who are participating in a clinical study
- Relatives, partner or staff of any clinical site personnel

Disease-related

- Evidence of skin conditions (e.g. eczema) other than PPP / psoriasis that would interfere with evaluations of the effect of study medication on PPP or psoriasis.
- Laboratory values from routine blood test taken within the 8 weeks prior to screening with any of the following:
 - Serum creatinine $>1.4 \times$ upper limit of normal (ULN) for age and gender
 - Estimated Glomerular Filtration Rate (eGFR) $< 30 \text{ mL/min}/1.73 \text{ m}^2$ according to the CKD-EPI equation
- Pustular psoriasis lesions on the part of body other than hands or feet
- Significant concurrent medical conditions at the time of screening, including:
 - Risk factors for renal toxicity (renal inflammation)
 - Severe hepatic dysfunction
 - Unstable angina pectoris
 - Uncompensated congestive heart failure
 - Severe pulmonary disease requiring hospitalization or supplemental oxygen therapy
 - Immunodeficiency disorders: primary or secondary
 - Known positive HIV test result, hepatitis B surface (HBS) antigen or hepatitis C (HCV) test result
 - Uncontrolled Insulin-dependent diabetes mellitus
 - Cancer or history of cancer (except for resected cutaneous basal cell or squamous cell carcinoma) in the last 5 years
 - Open cutaneous ulcers
- Any condition that, in the judgment of the investigator, might cause this study to be detrimental to the patient.

Medication-related

- Ultraviolet B (UVB) therapy, topical steroids, topical calcineurin inhibitors, topical Vitamin A or D analog preparations, or anthralin within 14 days of baseline
Exceptions: low potency topical corticosteroids (class I and II, according to European classification for potency of topical corticosteroids) will be allowed as therapy for the face, groin, axillae in accordance with the manufacturer's suggested usage dose

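### Section 6.2 says patients with moderate / severe kidney disorders and with liver disorders are kept out, but the exclusion criteria in 9.1.2 and the synopsis exclude less, most clearly for the liver

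*Protocol*

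**What the plan says.** Protocol 6.2 draws on the risk management plan summary for apremilast. It refers to the "exclusion of patients with moderate / severe kidney disorders, liver disorders, children and pregnant or breastfeeding patients from clinical trials" and concludes that for these patients "there is no information on safety or effectiveness" of the drug. It then says of this trial: "However, these patient groups will also be excluded for the clinical study presented here".

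Eligibility itself is set in section 9.1: "Patients will be enrolled if all inclusion and none of the exclusion criteria are met". The parts of 9.1.2 that bear on kidney and liver, repeated in the synopsis, are:

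- two laboratory limits from a routine blood test: creatinine above 1.4 times the ULN for age and gender, and CKD-EPI eGFR below 30 mL/min/1.73 m²;
- under an open-ended list of significant concurrent conditions: risk factors for renal toxicity, glossed as renal inflammation; "Severe hepatic dysfunction"; and a known positive hepatitis B surface antigen or hepatitis C test;
- a general clause that lets the investigator exclude anyone for whom the study might be detrimental.

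No liver laboratory value has a limit. The flow chart row "Results of routine blood test / urinalysis available" is marked at Visit 1 only.

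**The concern.** Section 6.2 is the protocol's risk-benefit statement, in a document that the ethics committee and competent authority must approve. It tells them that groups without safety data are kept out. If the criteria admit some of those patients, that assurance is not true as written. A site could follow 9.1.2 correctly and enrol a patient whom 6.2 describes as both lacking data and excluded.

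Such a patient would be assigned 30 mg twice daily to week 20. Section 10.7 allows a reduction to one tablet a day for at most 5 days in a row or 10 in total. No routine blood test is scheduled after screening. Safety is a secondary objective, assessed through adverse events, vital signs and physical examination.

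**Working it through.** The mismatch is one of wording, so the first step is to set the groups named in 6.2 against the criteria.

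| Group in 6.2 | Criterion in 9.1.1 / 9.1.2 | Does 6.2 hold? |
|---|---|---|
| Children | "Male and female patients aged 18 years or more at screening visit" | Yes |
| Pregnant or breast-feeding | Excluded | Yes |
| Liver disorders | Severe dysfunction; known positive hepatitis B or C test | In part |
| Moderate / severe kidney disorders | Creatinine >1.4 × ULN; eGFR <30; renal inflammation | In part, depending on what moderate means |

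**Liver.** It is unclear whether moderate / severe in 6.2 also qualifies liver disorders.

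- If it does, 6.2 excludes moderate and severe. The criteria exclude severe, so moderate dysfunction is left eligible.
- If it does not, 6.2 excludes all liver disorders. The criteria then leave mild and moderate dysfunction eligible.

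Apart from known hepatitis B or C, moderate dysfunction is eligible on both readings. No outside figure is needed.

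**Kidney.** This part is illustrative, because four inputs are not in the documents: the meaning of moderate (eGFR 30-59, or 30-44 as a narrower alternative); the creatinine ULNs (0.8-1.1 mg/dL for women, 1.1-1.3 for men); the version of CKD-EPI (2009 here); and ULNs held constant over age, although the criterion refers to a ULN for age and gender.

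The question is what eGFR a patient has at exactly 1.4 × ULN, the highest creatinine still eligible. For creatinine S above k:

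eGFR = 141 × (S/k)^−1.209 × 0.993^age (× 1.018 if female), with k = 0.7 for women and 0.9 for men.

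- Man aged 50, ULN 1.2: S = 1.4 × 1.2 = 1.68. eGFR = 141 × (1.68/0.9)^−1.209 × 0.993^50 = 46.7.
- Woman aged 50, ULN 1.0: S = 1.4 × 1.0 = 1.40. eGFR = 141 × (1.40/0.7)^−1.209 × 0.993^50 × 1.018 = 43.7.

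These two patients could enter with an eGFR from 46.7 or 43.7 upwards, so the top of the 30-59 band is eligible and the creatinine limit removes the rest. The 2021 form of the equation gives 49.2 and 45.8, with the same conclusion for 30-59.

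For ages 40, 50, 60 and 70 and seven ULNs (0.8, 0.9, 1.0, 1.1 for women; 1.1, 1.2, 1.3 for men), 4 × 7 = 28 combinations, the eGFR at the creatinine limit runs from 33.8 to 61.4:

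| eGFR at the creatinine limit | Combinations | Meaning |
|---|---|---|
| below 60 | 27 of 28 | part of 30-59 is eligible |
| below 45 | 13 of 28 | part of 30-44 is eligible |
| below 30 | 0 of 28 | the eGFR limit would add an exclusion |

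These are combinations of assumptions, not proportions of patients. The gap closes for some young adults: a man aged 20 with ULN 1.1 is at 64.0 at the creatinine limit, so for him the whole 30-59 band is excluded.

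**The case against.** The strongest reply is that no site gets conflicting instructions. Section 6.2 is background, 9.1 says which lists decide enrolment, and 9.1.2 and the synopsis agree with each other. The list of concurrent conditions is open-ended, and the investigator can exclude anyone at risk. All of that is correct, and it limits the point to the truth of the 6.2 statement. It does not remove the point. Discretion can keep individuals out, whereas 6.2 says the groups will be excluded, and naming severe dysfunction suggests to a site that milder dysfunction is acceptable.

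A second reply is that the kidney half depends on definitions that the protocol does not give. This stands. On the narrower meaning of moderate, fewer than half of the 28 combinations leave any of the band eligible, and the creatinine limit already does much of the excluding. The kidney figures can only illustrate.

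A reader might also infer three stronger things that the documents do not support:

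- *That these patients would be harmed, or that 30 mg twice daily is wrong for them.* The documents do not allow that judgement.
- *That the study report would conceal them.* The SAP has no laboratory table or listing, but protocol 12.3.2 requires concomitant diseases to be recorded, 12.2.3 requires significant pre-enrolment findings in the medical history, and SAP table 14.1.7 summarises medical history.
- *That the eGFR limit must rise to 60 or 45.* Nothing in the documents settles where it should lie.

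**Conclusion.** The point holds as a minor inconsistency. Section 6.2 claims a wider exclusion than 9.1.2 and the synopsis deliver. For the liver this follows from the text alone: at least moderate dysfunction, outside known hepatitis B or C, stays eligible. For the kidney it is conditional: if moderate means eGFR 30-59, and ULNs are in the usual range, part of that band stays eligible in most of the combinations examined.

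The documents do not say how many patients with palmoplantar pustulosis fall into either group, so the effect among 20 patients cannot be sized. The sample size, which was not derived statistically, and the primary analysis are unaffected.

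**What to change.** Choose one of two routes and make the sections agree.

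1. **Bring the criteria towards 6.2.** In 9.1.2 and the synopsis, extend the liver item to *Moderate or severe hepatic dysfunction*, and use the same severity words for the liver in 6.2. In 6.2, state the renal limit that actually applies: creatinine above 1.4 × ULN or eGFR below 30.
2. **Bring 6.2 to the criteria.** If the wider eligibility is intended, leave 9.1.2 and correct the 6.2 sentence to say that patients with moderate renal impairment and non-severe liver disorders may be enrolled, and on what safety information.

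Raising the eGFR cut-off is open to the sponsor but is not needed for consistency.

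The cost is a short amendment, to 6.2, 9.1.2 and the synopsis for the first route or to 6.2 alone for the second. No new test is required; moderate liver dysfunction would be judged clinically, as severe dysfunction is now. The first route may make a few patients with moderate liver dysfunction ineligible in a rare disease, a number the documents do not give. The second costs no patients but gives up the protection that 6.2 now claims.
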